2.4 Exploratory Endpoints

Exploratory objectives are:

- To investigate the effect of treatment with glepaglutide on nutritional status, organ function and fluid balance
- To investigate the effect of treatment with glepaglutide on patient reported outcomes (PROs)
- To investigate the microbiome composition of subjects with SBS
- To investigate the pharmacokinetics of glepaglutide.

Exploratory endpoints are:

• Body weight: Change from baseline to Week 12, 24 and 52.

Body weight (kg) will be analyzed at Baseline, Week 12, Week 24 and Week 52 (EOT). The change of body weight (kg) from baseline to Week 12, Week 24 and Week 52 (EOT) is calculated as described in Section 2.1.2 and will be analyzed at Week 12, Week 24 and Week 52 (EOT).

• Body composition (lean body mass, fat mass and bone mineral content) by dual-energy X-ray absorptiometry (DEXA): Change from baseline to Week 12, 24 and 52.

The total lean body mass, total fat mass, fat percent, total bone mineral content, bone mineral density as well as the T-score and Z-score will be measured using DEXA scan.

During the whole trial, four DEXA scans will be performed: during the MBS at the baseline Visit (V1), at Week 12 (V6), during the MBS at Week 24 (V9) and at Week 52 (V12). During the MBS at V1 and V9, the DEXA scan may be done either on Day 2 or on Day 3.

The parameters

- Lean body mass (kg)
- Fat mass (kg)
- Bone mineral content (kg)

will be analyzed at Baseline, Week 12, Week 24 and Week 52 (EOT). Changes from baseline to Week 12, Week 24 and Week 52 (EOT) are calculated as described in Section 2.1.2 and will be analyzed at Week 12, Week 24 and Week 52 (EOT).

DEXA parameters fat percent, bone mineral density, T-score and Z-score will only be listed.

• Citrulline: Change from baseline to Week 12, 24 and 52.

Citrulline will be analyzed at Baseline, Week 12, Week 24 and Week 52 (EOT). Changes from baseline to Week 12, Week 24 and Week 52 (EOT) are calculated as described in Section 2.1.2 and will be analyzed at Week 12, Week 24 and Week 52 (EOT).

• Aldosterone: Change from baseline to Week 12, 24 and 52.

Aldosterone will be analyzed at Baseline, Week 12, Week 24, Week 52 (EOT). Changes from baseline to Week 12, Week 24 and Week 52 (EOT) are calculated as described in Section 2.1.2 and will be analyzed at Week 12, Week 24 and Week 52 (EOT).

• Estimated glomerular filtration rate (eGFR), creatinine clearance and liver function tests: Change from baseline to Week 12, 24 and 52.

Estimated glomerular filtration rate (eGFR) is calculated based on the modification of diet in renal disease (MDRD) formula.

Statistical Analysis Plan

The parameters eGFR, estimated creatinine clearance (assessed by biochemistry laboratory) and liver function parameters (ALT, AST, ALP, albumin and total bilirubin) will be analyzed at Baseline, Week 12, Week 24 and Week 52 (EOT). Changes from baseline to Week 12, Week 24 and Week 52 (EOT) are calculated as described in Section 2.1.2 and will be analyzed at Week 12, Week 24 and Week 52 (EOT).

• Hemoglobin A1c (HbA1c): Change from baseline to Week 4, 12, 24 and 52.

This endpoint will only be analyzed for the subgroup of patients who reach Week 4 after protocol amendment #2 has become effective. In case of a missing Baseline value, it will be replaced by the HbA1c value at Week 4 and the changes from baseline will instead be calculated from Week 4. For the presentation of this parameter by visit, all assessments will be analyzed at the timepoint they were taken.

HbA1c will be analyzed at Baseline, Week 4, Week 12, Week 24, Week 52 (EOT). Changes from baseline to Week 4, Week 12, Week 24 and Week 52 (EOT) are calculated as described in Section 2.1.2 and will be analyzed at Week 4, Week 12, Week 24 and Week 52 (EOT).

- PRO: patient's global impression of change (PGIC). At Week 12, 24 and 52.
 PRO: patient's global impression of change (PGIC) will be analyzed at Week 12, Week 24, and Week 52 (EOT).
- PRO: SBS -impact scale (SBS-I) and EQ-5D-5L. Change from baseline to Week 12, 24 and to Week 52.

The SBS-I has the following eight items

- 1. How affected have you been by gastrointestinal symptoms related to SBS such as diarrhea, nausea or bloating in the last week?
- 2. How affected have you been by pain in your muscles or bones due to your illness (SBS) in the last week?
- 3. How affected have you been by pain in your abdomen due to your illness (SBS) in the last week?
- 4. How exhausted or tired have you been due to your illness (SBS) in the last week?
- 5. How much has your illness (SBS) affected your sleep in the last week?
- 6. To what degree has your illness (SBS) interfered with the things you wanted to do in the last week?
- 7. How much has your illness (SBS) affected your mood in the last week?
- 8. How affected have you been by stress or anxiety related to SBS in the last week?

Each item is rated on a discrete scale from 0 to 10. Each SBS-I item score will be analyzed overall and separately for patients with SBS-II and patients with SBS-IF at Baseline, Week 12, Week 24 and Week 52 (EOT). Changes from baseline to Week 12, Week 24 and Week 52 (EOT) are calculated as described in Section 2.1.2 and will be analyzed at Week 12, Week 24 and Week 52 (EOT).

The EQ-5D-5L has five domains (mobility, self-care, usual activities, pain/discomfort, anxiety/depression) with the following five response levels: no problems (1), slight problems (2), moderate problems (3), severe problems (4), and unable to/extreme problems to do something (5). Additionally, the current health should be assessed on a visual analogue scale between 0 and 100.

Furthermore, an EQ-5D-5L index value summarizing the values from all domains will be analyzed. It is calculated based on the Danish standardisation study for the EQ-5D-5L (Jensen, C.E. et al. The Danish EQ-5D-5L Value Set: A Hybrid Model Using cTTO and DCE Data. Appl Health Econ Health Policy 19, 579–591 (2021). https://doi.org/10.1007/s40258-021-00639-3). If all domain values are non-missing, it is calculated using the following algorithm:

```
IF (mobility=1) THEN mo=0
IF (mobility=2) THEN mo=0.041
IF (mobility=3) THEN mo=0.054
IF (mobility=4) THEN mo=0.157
IF (mobility=5) THEN mo=0.220
IF (selfcare=1) THEN sc=0
IF (selfcare=2) THEN sc=0.035
IF (selfcare=3) THEN sc=0.050
IF (selfcare=4) THEN sc=0.144
IF (selfcare=5) THEN sc=0.209
IF (usual activities=1) THEN ua=0
IF (usual activities=2) THEN ua=0.033
IF (usual activities=3) THEN ua=0.040
IF (usual activities=4) THEN ua=0.139
IF (usual activities=5) THEN ua=0.174
IF (pain discomfort=1) THEN pd=0
IF (pain discomfort=2) THEN pd=0.048
IF (pain discomfort=3) THEN pd=0.094
IF (pain discomfort=4) THEN pd=0.381
IF (pain discomfort=5) THEN pd=0.537
IF (anxiety depression=1) THEN ad=0
IF (anxiety depression=2) THEN ad=0.072
IF (anxiety depression=3) THEN ad=0.191
IF (anxiety depression=4) THEN ad=0.430
IF (anxiety depression=5) THEN ad=0.618
total = mo + sc + ua + pd + ad
EQ5D5L Index Value = 1-total
```

In case any of the domain values is missing, the index value will be missing.

The EQ-5D-5L domains, the current health and the index value will be analyzed at Baseline, Week 12, Week 24 and Week 52 (EOT). Changes from baseline to Week 12, Week 24 and Week 52 (EOT) of the five domains will be analyzed at Week 12, Week 24 and Week 52 (EOT). Changes from baseline to Week 12, Week 24 and Week 52 (EOT) of the current health are calculated as described in Section 2.1.2 and will be analyzed at Week 12, Week 24 and Week 52 (EOT).

• *Pharmacokinetic (PK) parameter (C_{trough}).*

Pharmacokinetic analysis will be done for the parent drug, the metabolites M1 and M2 and the constructed analyte glepaglutide (defined as parent drug + M1 + M2). PK sampling will be done at V1, V4, V6, V9 (six samples: one sample each at MBS Day 1 and Day 4, and two samples each on Day 2 and Day 3 [at least 6h in between sampling on Day 2 and Day 3]), V12 and FU.

Descriptive statistics will be provided for C_{trough} for Week 4, Week 12, Week 24 and Week 52 (EOT).

Results from V4, V6, V9 and V12 samples will be considered and analyzed as trough levels, as long as trial product was not administered within the last at least 6*24=144 hours prior to drawing the sample. At V9, determine all samples which fulfill the criterion above (trial product was not administered within the last at least 6x24h=144h) and select for analysis the sample for which time since last trial product administration is closest to 7*24=168.

All PK concentrations will be listed.

• The luminal- and mucosae-associated microbiota of patients with SBS from baseline to Week 24.

Luminal- and mucosae-associated microbiota may be assessed at the MBS at baseline (V1) and Week 24 (V9).

Luminal- and mucosae-associated microbiota may be analyzed at Baseline and Week 24. The change from baseline to Week 24 is calculated as described in Section 2.1.2 and may be analyzed at Baseline and Week 24.

• Urinary excretion of electrolytes (sodium, potassium, calcium, magnesium) and urea: Change from baseline to Week 24.

Urinary excretion of electrolytes: Sodium (mmol/d) is derived as described in Section 2.2.3 based on the eCRF item Urinary electrolytes: Sodium (mmol/d).

Change from baseline to Week 24 for Urinary excretion of electrolytes: Sodium (mmol/d) is calculated as described in Section 2.1.2 and analyzed at Week 24.

Furthermore,

- Urinary excretion of electrolytes: Potassium (mmol/d) [based on eCRF information "Urinary electrolytes: Potassium (mmol/d)"],
- Urinary excretion of electrolytes: Calcium (mmol/d) [based on eCRF information "Urinary electrolytes: Calcium (mmol/d)"],
- Urinary excretion of electrolytes: Magnesium (mmol/d) [based on eCRF information "Urinary electrolytes: Magnesium (mmol/d)"], and
- Urinary excretion of electrolytes: Urea (mmol/d) [based on eCRF information "Urinary electrolytes: Urea (mmol/d)"]

as well as their changes from baseline to Week 24 are calculated and analyzed analogously to Urinary excretion of electrolytes: Sodium (mmol/d) and its change from baseline to Week 24.

• Fluid Composite Effect: Change from baseline to Week 12, 24 and 52.

The fluid composite effect has been defined as parenteral volume + oral fluid volume – urine volume. Thus, fluid composite effect (L/d) at a certain visit will be calculated as:

Fluid composite effect (L/d) = [current PS volume (L/week)/7] + [oral fluid volume (L/d)] - [urine volume (L/d)].

Oral fluid volume (L/d) is based on 48-hour total drinking volume during the 48-hour urine collection period in the week prior to a visit (V2 to V8 and V10 to V12) or on the 48-hour total drinking volume during the MBS at V1 and V9:

Oral fluid volume (L/d) = [48-hour total drinking volume (mL)/1000]/2

Urine volume (L/d) is based on the total urine volume during the 48-hour urine collection period in the week prior to a visit (V2 to V8 and V10 to V12) or on the 48-hour urine volume collected during the MBS at V1 and V9.:

Urine volume (L/d) = [48-hour total urine volume (mL)/1000]/2

Current PS volume (L/week) will be derived as described in Section 2.3.2.

Fluid composite effect (L/d) will be analyzed at Baseline, Week 12, Week 24 and Week 52 (EOT). Changes from baseline to Week 12, Week 24 and Week 52 (EOT) are calculated as described in Section 2.1.2 and will be analyzed at Week 12, Week 24 and Week 52 (EOT).

• Drinking volume during 48-hour periods: Change from Week 24 to 52.

Drinking volume during 48-hour periods is based on the eCRF item Drinking volume: 48-hour total drinking volume (mL) and will be analyzed at Baseline, Week 24 and Week 52 (EOT). Change from Week 24 to Week 52 (EOT) for Drinking volume during 48-hour periods is calculated as described in Section 2.1.2 and will be analyzed at Week 52 (EOT).

- For patients with SBS-IF only:
 - Weekly PS volume: Change from baseline to Week 52.

Calculation of current weekly PS volume has been described in Section 2.3.2.

Additionally to the analysis time points stated in Section 2.3.2, weekly PS volume will be analyzed at Week 52 (EOT), and the change of weekly PS volume from baseline to Week 52 (EOT) will be analyzed at Week 52 (EOT).

• Weekly PS macronutrients (total and individual energy content of carbohydrates, lipids and proteins) and electrolytes (sodium, potassium and magnesium): Change from baseline to Week 52.

Calculation of weekly PS macronutrients and electrolytes has been described in Section 2.3.2.

Additionally to the analysis time points stated in Section 2.3.2, weekly PS macronutrients will be analyzed at Week 52 (EOT), and the change of weekly PS macronutrients from baseline to Week 52 (EOT) will be analyzed at Week 52 (EOT).

• Weekly days on PS: Change from baseline to Week 12, 24 and 52.

The number of weekly days on PS is derived based on the eCRF page "Diary PS use" as the sum of days in the week prior to the visit (date of visit -1 to date of visit -7) for which a volume has been documented (i.e. > 0 mL and not unknown) for at least one PS bag identifier. Here the date of visit used at baseline is the date of Visit 1 - Week 0 - Day 4 as documented in the eCRF. At Week 24, the date of Visit 9 - Week 24 - Day 4 is used. The number of weekly days on PS for a certain visit after baseline will be missing in case only unknown volumes have been documented for at least one day or if

the Diary PS use page is missing for at least one day in the time interval used for calculation.

In case information on Diary PS use in the week before the baseline visit is available for less than seven days, the number of weekly days on PS is derived based on prescribed PS over the week before the date of Visit 1 – Week 0 – Day 4. Thus, all PS prescriptions which are valid on date of "Visit 1 – Week 0 – Day 3" are determined. The number of weekly days on PS at baseline is then calculated as the average over the number of days per week as documented in the eCRF for all these prescriptions.

Weekly days on PS will be analyzed at Baseline, Week 12, Week 24 and Week 52 (EOT). Changes from baseline to Week 12, Week 24 and Week 52 (EOT) are calculated as described in Section 2.1.2 and will be analyzed at Week 12, Week 24 and Week 52 (EOT).

- For patients with SBS with intestinal insufficiency (SBS-II) only:
 - *Urine output: Change from baseline to Week 12, 24 and 52.*

Total 48-hour urine volumes will be analyzed at Baseline, Week 12, Week 24 and Week 52 (EOT). Changes from baseline to Week 12, Week 24 and Week 52 (EOT) will be calculated as described in Section 2.1.2 and analyzed at Week 12, Week 24 and Week 52 (EOT). The change from Week 24 to Week 52 (EOT) will be calculated as described in Section 2.1.2 and analyzed at Week 52 (EOT).

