### **Exploratory Endpoints**

- Body weight: Change from baseline to Week 12, 24 and 52.
- Body composition (lean body mass, fat mass and bone mineral content) by dual-energy X-ray absorptiometry (DEXA): Change from baseline to Week 12, 24 and 52.
- Citrulline: Change from baseline to Week 12, 24 and 52.
- Aldosterone: Change from baseline to Week 12, 24 and 52.
- Estimated glomerular filtration rate (eGFR), creatinine clearance and liver function tests: Change from baseline to Week 12, 24 and 52.
- Hemoglobin A1c (HbA1c): Change from baseline to Week 4, 12, 24 and 52.
- Patient reported outcome (PRO) (patient's global impression of change [PGIC]). At Week 12, 24 and 52.
- PRO: SBS -impact scale (SBS-I) and EQ-5D-5L. Change from baseline to Week 12, 24 and to Week 52.
- Pharmacokinetic (PK) parameters (t1/2 and Ctrough).
- To investigate the luminal- and mucosae-associated microbiota of patients with SBS from baseline to Week 24.
- Urinary excretion of electrolytes (sodium, potassium, calcium, magnesium) and urea: Change from baseline to Week 24.
- Fluid Composite Effect: Change from baseline to Week 12, 24 and 52.
- Drinking volume during 48-hour periods: Change from Week 24 to 52.
- For patients with SBS-IF only:
  - o Weekly PS volume: Change from baseline to Week 52.
  - Weekly PS macronutrients (carbohydrates, lipids and proteins) and electrolytes (sodium, potassium and magnesium): Change from baseline to Week 52.
  - o Weekly days on PS: Change from baseline to Week 12, 24 and 52.

- For patients with SBS-II only:
  - o Urine output: Change from baseline to Week 12, 24 and 52.

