# 8.2.15 Hemoglobin A1c

Blood samples for measurement of hemoglobin A1c (HbA1c) will be drawn prior to first dose of trial product at Visit 1 and prior to administration of trial product at other visits (if dosing occurs on the visit day). Details are provided in the laboratory manual. Analysis will be performed at the local laboratory at the trial site. Samples will be destroyed after analysis.

Changes from baseline to Week 4 (Visit 4), Week 12 (Visit 6), Week 24 (Visit 9) and Week 52 (Visit 12) will be measured.

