2.1.2.1 Change from baseline

The absolute change from baseline (V1) to any visit during the treatment phase or to the follow-up (FU) visit will be calculated as the value at the visit minus the baseline value. If any of the two values is missing, the absolute change from baseline will be missing.

The relative change (fold increase) [%] is calculated by dividing the absolute change by the baseline value and by multiplying this ratio by 100 to obtain a percentage. If the absolute change is missing or if the baseline value is zero, the fold increase from baseline will be missing.

Concerning efficacy parameters of the 48-hour metabolic balance studies (MBS, see Section 2.2.1) for which separate measurements are available for the first and second 24-hour period, absolute changes from baseline to Week 24 (V9) are calculated as average of the measures obtained during the first 24-hour period (documented in the eCRF at Day 2) and during the second 24-hour period (documented in the eCRF at Day 3) of the MBS at V9 minus the average of the measures obtained during the first and second 24-hour period of the MBS at V1 (see calculation formula in Section 2.2.1). Dealing with missing measurements for one of the 24-hour periods at V1 (or V9, respectively) is described in Section 2.2.1. If any of the two averaged values is missing, the absolute change from baseline to Week 24 (V9) will be missing.

The baseline value will be the value tabulated for the 'Baseline' visit as described in Section 2.1.1.

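### Replacing a missing HbA1c baseline with the on-treatment Week 4 value gives those patients a Week 4 change of exactly zero and mixes unlabelled changes from Week 4 into the change-from-baseline table.

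*SAP*

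**What the plan says.** The protocol's exploratory endpoint is "Hemoglobin A1c (HbA1c): Change from baseline to Week 4, 12, 24 and 52". Under Protocol Section 8.2.15 the baseline sample "will be drawn prior to first dose of trial product at Visit 1". A footnote to that section limits HbA1c sampling to patients who reach Week 4 once amendment #2 is in force. A patient who had passed Visit 1 but not Week 4 on that date may therefore have no baseline sample.

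SAP Section 2.4 restricts the HbA1c analysis to the same subgroup and adds a substitution rule: "In case of a missing Baseline value, it will be replaced by the HbA1c value at Week 4". The same sentence moves the reference point for such patients, stating that "the changes from baseline will instead be calculated from Week 4". It then says that values shown by visit stay at the time they were taken. The following paragraph reads "Changes from baseline to Week 4, Week 12, Week 24 and Week 52 (EOT) are calculated as described in Section 2.1.2", with no exception at Week 4 for substituted patients.

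SAP Section 2.1.2.1, to which that paragraph refers, says the absolute change "will be calculated as the value at the visit minus the baseline value". It also says: "If any of the two values is missing, the absolute change from baseline will be missing". And: "The baseline value will be the value tabulated for the 'Baseline' visit as described in Section 2.1.1".

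In SAP Appendix A, Table 2-3.6.1 carries the HbA1c changes under a change-from-baseline title, with no footnote or separate row for substituted patients. Table 2-3.6.2 carries the by-visit values. SAP Section 6 does not list the substitution among the changes from protocol.

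**The concern.** A baseline is meant to be a pre-treatment reference. Weekly dosing starts at the end of Visit 1, so on the nominal schedule a Week 4 sample follows about four doses. Week 4 is also one of the endpoint's own analysis visits, so the substituted value is compared with itself there. The zero that results is arithmetic and carries no information about the patient, yet it would count as a valid observation in the mean, standard deviation and quartiles of the SAP Section 7.1 table format.

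At the later visits the label is inaccurate for these patients: their changes run from Week 4, not from before treatment. In a trial planned for 6 to 16 patients, one or two such entries are enough to alter a descriptive summary. At stake is the reading of a single exploratory table.

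**Working it through.** The documents give no sample size, power or numerical result for HbA1c, so there is no stated figure to reproduce. The check applies the SAP's own rules.

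**Inputs**
- Substitution: baseline B is set to the Week 4 value W4 (SAP 2.4).
- Change at a visit = visit value − B (SAP 2.1.2.1).
- Visits at which change is analyzed: Weeks 4, 12, 24 and 52 (SAP 2.4).
- n: the number of patients in the HbA1c analysis with a Week 4 change. The protocol plans 10 patients (Section 9.2), or 6 to 16 (Synopsis). The HbA1c subgroup may be smaller.
- k: the number substituted. It is not in the documents and may be zero.

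**Week 4**

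For a substituted patient, change = W4 − W4 = 0, whatever happened in the first four weeks.

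The tabulated mean is (sum of the n − k observed changes + k × 0) / n = [(n − k)/n] × the mean among patients with a real baseline. This is exact and needs no assumption about the substituted patients' true changes.

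| n (assumed) | k = 0 | k = 1 | k = 2 | k = 3 |
|---|---|---|---|---|
| 6 | 1.0 | 0.833 | 0.667 | 0.5 |
| 10 | 1.0 | 0.9 | 0.8 | 0.7 |
| 16 | 1.0 | 0.938 | 0.875 | 0.812 |

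A simulation with n = 10, true mean change 1 and SD 1 agrees. The tabulated mean is 0.80 for k = 2 and 0.70 for k = 3, against 1.00 when those patients are left missing.

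SAP Section 4.1 also splits tables by SBS type. With 10 patients divided equally, one substitution in a group of 5 gives (5 − 1)/5 = 0.8 in that group.

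**Weeks 12, 24 and 52**

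For a substituted patient, with W0 the unobserved pre-treatment value:

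W12 − W4 = (W12 − W0) − (W4 − W0), and likewise for Weeks 24 and 52.

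The entry therefore differs from the true change by whatever happened in the first four weeks. The intervals are 12 − 4 = 8, 24 − 4 = 20 and 52 − 4 = 48 weeks, pooled with intervals of 12, 24 and 52 weeks.

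The direction of the error depends on W4 − W0, on which the documents give nothing. Two sets of assumed values show that it can go either way:
- W0 = 40, W4 = 42, W12 = 38: the true change is −2 and the tabulated change is −4, which is further from zero.
- W0 = 42, W4 = 40, W12 = 38: the true change is −4 and the tabulated change is −2, which is nearer zero.

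**The case against.** The rule has a reason. HbA1c was added by amendment, some patients may lack a baseline through no fault of theirs, and using Week 4 keeps their later on-treatment data in a very small trial. The rule is prespecified and stated openly. That explains why the sponsor wanted to use these data. It does not justify a zero at Week 4 or pooling without a label.

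The zero could also be disputed. Calculating from Week 4 might be meant to start these patients' changes after Week 4, with no Week 4 entry. That intention is plausible, but the SAP does not state it, and a programmer following the next paragraph would produce zeros. At the least, the text is ambiguous and needs a sentence to settle it.

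A reader might infer three stronger conclusions, none of which the documents support:
- *The SAP breaks its own missing-data rule.* Section 4.5 allows replacement where it is specified, and Section 2.4 specifies it. This is a stated exception to the default in Section 2.1.2.1.
- *The mean change is pulled toward zero at every visit.* That is certain only at Week 4. Later the direction is unknown.
- *An effect on glycemia is hidden.* By-visit values stay at their true times and appear in Table 2-3.6.2, and Section 4.1 promises listings of all eCRF data.

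**Conclusion.** The concern holds in a narrow form. Read literally, the rule gives every substituted patient a Week 4 HbA1c change of exactly zero and so shrinks the mean Week 4 change by the factor (n-k)/n. The factor is 0.9, 0.8 or 0.7 for one, two or three substitutions among an assumed 10 patients, and 1.0 if there are none. At later visits these patients contribute changes that omit their first four weeks of treatment, under a title that says otherwise. The size and direction of that error cannot be determined from the documents.

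The conclusion rests on the literal reading of Section 2.4, and its practical size rests on k, which is not given. The consequence is small. SAP Section 4.3.4 makes the exploratory endpoints descriptive only, and no primary or key secondary test is touched. The change is worth making because it is easy.

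**What to change.** In SAP Section 2.4, delete the replacement of a missing HbA1c baseline by the Week 4 value, so that the default in Section 2.1.2.1 applies: with no Visit 1 value, change from baseline is missing at every visit. For these patients, report change from Week 4 to Weeks 12, 24 and 52 in a separate row of Table 2-3.6.1, labelled as change from Week 4 and calculated under the existing visit-to-visit definition in Section 2.1.2.2. Show no Week 4 change for them. State the number of patients in each row, which also discloses k.

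The cost is one deleted sentence, one added row and a smaller n for HbA1c change from baseline. No collected HbA1c value is lost, since the later on-treatment changes still appear under an accurate label.

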• A patient was enrolled despite it was later identified that some of the inclusion or exclusion criteria were violated. The Investigator must discuss with the Sponsor's Medical Monitor if it is safe for the patient to continue the trial treatment. If a patient prematurely discontinues trial treatment, the primary reason must be specified in the eCRF. If the patient continues in the trial without trial treatment, the intent should be to follow the patient to the extent possible according to the planned visit schedule and assessments with the purpose of following the safety and efficacy of the patients. Reason for visits not having been performed must be documented.

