### • PROs:

- Ocopies of PGIC, SBS-I and EQ-5D-5L questionnaires can be sent to the patients for completion, including the standard instructions for how to complete, date, and sign. The instructions include among other things the following notes; It is important the SBS-I is completed by the patient without assistance of family members.
- o Patients should:
  - Fill in the PROs and complete the questionnaires on the same day as the remote visit is scheduled, but prior to the site visit call.
  - Send a copy of completed PROs to site for review and entry into eCRF.
  - Bring original documents to site at next possible visit. These documents will be source data to be verified at that point. If source data is lost, then copies received will suffice.
- Trial product can be sent directly from the site to the patient's home
- Visit 9 can be postponed, until on-site visit is possible again. After 24 weeks of treatment, the patient will be in a stable treatment, and postponing the visits is not expected to affect the assessments
- The EoT visit can be postponed (time window can be extended up to + 8 weeks)

Deviations from the protocol caused by circumstances related to the pandemic will be documented. Handling of data affected by the pandemic situation will, if applicable, be addressed in the statistical analysis plan.

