4 STATISTICAL EVALUATION

4.1 General

The statistical analysis will be performed using the software package SAS® version 9.4 or higher.

Patient listings will be generated for all data items collected in the eCRF.

In general, data will be summarized using the following standard descriptive statistics: Continuous data will be summarized by presenting the number of non-missing observations, arithmetic mean and standard deviation (geometric mean and coefficient of variation (CV), where applicable), median, minimum, lower quartile, upper quartile and maximum. Categorical data will be summarized by presenting the number and percentage of patients for each category as well as the number of events (where applicable, e.g. for AEs).

As results of several analyses are not only of interest for the overall population, but also for patients with SBS-IF and patients with SBS-II separately, summary tables will present these two subgroups in separate columns [rows] in addition to a total column [row], unless this is not reasonable or feasible (e.g., in case of endpoints which cannot be calculated for one of the two subgroups, like PS-related endpoints). Where such subgroup analyses are of particular importance, this is explicitly stated again in the relevant sections of this SAP.

Changes from the methods planned in this SAP will be justified in the clinical trial report.

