4.2.4 Drug Exposure and Treatment Compliance

The selected dose for this trial is 10 mg glepaglutide once-weekly for 52 weeks. Summary tables presenting descriptive statistics will be provided for:

- Drug exposure
- Treatment compliance.

Drug exposure will be measured by the number of trial product administrations per patient.

Treatment compliance will be calculated by dividing the actual number of trial product administrations per patient by the number of trial product administrations theoretically to be applied during the patient's individual treatment period. That means, the actual number of trial product administrations per patient will be divided by [1 + the number of weeks until visit Week 52 (EOT)], whereby number of weeks is the integer part of {[date of Week 52 (EOT) visit – date of first administration of trial product] / 7}. The result will be multiplied by 100 to obtain a percentage.

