4.3.4 Evaluation of Exploratory Endpoints

Exploratory endpoints (as defined in Section 2.4) will be analyzed using descriptive summary statistics based on the FAS.

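### Ctrough is defined by a minimum of 144 h since the last dose with no maximum, so missed-dose and off-treatment concentrations are summarized as troughs

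*SAP*

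**What the plan says.** The SAP's pharmacokinetic endpoint in section 2.4 takes results from Visits 4, 6, 9 and 12 as trough levels "as long as trial product was not administered within the last at least 6*24=144 hours prior to drawing the sample". Visit 9 has six samples, and there the analyst is told to find those that meet this criterion and "select for analysis the sample for which time since last trial product administration is closest to 7*24=168" h. The output is stated as "Descriptive statistics will be provided for C_{trough} for Week 4, Week 12, Week 24 and Week 52 (EOT").

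Four other provisions decide who enters those summaries:

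- Dosing is weekly (SAP 4.2.4: "The selected dose for this trial is 10 mg glepaglutide once-weekly for 52 weeks"), so the nominal trough is at 168 h.
- Exploratory endpoints "will be analyzed using descriptive summary statistics based on the FAS" (SAP 4.3.4). The FAS requires one dose, so poor compliance or stopping excludes nobody.
- SAP 2.1.1.1 presents Visit 12 data twice: under Week 52 for completers and under EOT for all patients. A patient who withdraws has the withdrawal visit recorded as the EOT examination.
- Protocol 7.1 asks patients who stop trial product to keep attending. Its text beginning "If the patient continues in the trial without trial treatment" intends them to follow the planned visits and assessments.

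Protocol Table 3 and section 8.6 ask for pre-dose sampling and recorded sample times. Neither sets a maximum time since dosing.

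**The concern.** A trough is the concentration at the end of a dosing interval during continued dosing. The SAP guards against samples drawn too early in the interval but not against samples drawn long after it has ended. The tolerance around 168 h is 24 h on the early side and unlimited on the late side.

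Section 6 of the SAP drops the half-life, so Ctrough is the only PK parameter left, tabulated for four analytes (tables 2-3.9.1 to 2-3.9.4). It also bears on a question the protocol raises itself: section 4.3.2 expects that concentrations may fall below the effective level late in each weekly interval, and section 2.3.1 names underdosing as a risk. A summary that mixes true troughs with washout values answers that question less well.

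**Working it through.** **The SAP's own limits.** 6 × 24 = 144 h and 7 × 24 = 168 h. Both reproduce.

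**The written rule applied (eligible if time since last dose is at least 144 h).**

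| Situation | Time since last dose | Counts as trough? |
|---|---|---|
| Dosed 2 days ago | 48 h | no |
| On schedule | 168 h | yes |
| One dose missed and not made up | 336 h | yes |
| Two doses missed | 504 h | yes |
| Stopped 4 weeks earlier | 672 h | yes |
| Stopped at Week 24, sampled at Week 52 | 28 × 168 = 4704 h | yes |

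**Visit 9.** Suppose one dose was missed and the six samples fall at 264, 288, 294, 312, 318 and 336 h. All qualify, and the closest-to-168 h instruction picks 264 h. It ranks the candidates but rejects none as too late.

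**Which rows are exposed.** A patient who has stopped trial product is kept out of the Week 52 row but enters the EOT row. For Visits 4, 6 and 9 the documents disagree. SAP 4.3.1 says treatment-phase data collection ends on withdrawal from the treatment phase, whereas Protocol 7.1 keeps such patients in the schedule. How many off-treatment samples would arise there cannot be settled from the text.

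**Size, off-drug value.** If one patient contributes about zero and the other n − 1 are at the usual level, the arithmetic mean falls by 1/n: 1/10 = 10% and 1/8 = 12.5%. Eight is the FAS target and ten the planned enrolment in Protocol 9.2. Here n is the number of qualifying samples in the row, which can be smaller than the FAS.

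**Size, sample at 336 h.** Assume first-order decline, so the ratio to the 168 h level is r = 2^(−(336 − 168)/t½), and the mean of 8 falls by (1 − r)/8. The half-lives are assumptions.

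| Assumed t½ | r at 336 h | Fall in mean, n = 8 | Fall in mean, n = 10 |
|---|---|---|---|
| 48 h | 0.088 | 11.4% | 9.1% |
| 100 h | 0.312 | 8.6% | 6.9% |
| 200 h | 0.559 | 5.5% | 4.4% |

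The geometric mean, which SAP 4.1 allows where applicable, is more sensitive. With n = 8 and t½ = 48 h it is multiplied by 0.088^(1/8) = 0.738, a fall of 26%.

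**The early side.** A sample at 144 h is 2^(24/t½) of the 168 h level: 141%, 118% and 109% for 48, 100 and 200 h. The rule admits these too.

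**The case against.** Several points on the other side are sound.

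- **Late visits.** A reader might infer that a delayed visit by itself yields a late trough, since Protocol 8.1.7 says "The EoT visit can be postponed (time window can be extended up to + 8 weeks". The documents do not support this. Patients dose weekly at home, Protocol 6.8 places the end of trial product at Visit 12, and the compliance formula in SAP 4.2.4 expects doses up to the actual EOT date. A late visit lengthens the interval only if dosing pauses.
- **Week 52.** A reader might also infer that stopped patients pull down the Week 52 figure. They do not, because that row is completers only.
- **Missed doses.** Protocol 6.4.1 tells patients to take a missed dose once they notice it, so a 336 h gap needs a dose that stays missed. At Visit 9 the selection rule softens the effect for patients still dosing.
- **Direction.** It is tempting to say that mean Ctrough is biased downward. Samples up to 24 h early push the other way, so the net direction is not established. What stands is that the early error is bounded and the late one is not.
- **Visibility.** All concentrations and doses are listed, immunogenicity listings carry the PK values, and the summaries include quartiles and the minimum. An attentive reader could spot a near-zero value and need not mistake it for an antibody effect. The listing does not, however, remove the value from the summary.

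None of this supplies a maximum time since dosing.

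**Conclusion.** The flaw holds as a defect in a stated rule: followed literally, it places missed-dose and off-treatment concentrations in the Ctrough summaries. The main effect is on the EOT row and on any off-treatment samples at Visits 4, 6 or 9. The Week 52 row is exposed only through doses that stayed missed.

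One near-zero value costs 10% to 12.5% of the arithmetic mean with 10 or 8 patients, almost regardless of half-life. The effect of a 336 h sample depends on half-lives that the documents do not give; Protocol 2.2 says they differ between glepaglutide and its metabolites, so the four tables would be affected unequally. How often such samples will occur is unknown. An apparent decline caused by antibodies is a possible misreading, not a predicted one.

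This is a minor point. The endpoint is exploratory and descriptive, and the primary and key secondary tests do not use it.

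**What to change.** In SAP 2.4, replace the one-sided criterion with a window plus a treatment condition: summarize a sample as Ctrough only if the patient has not permanently stopped trial product before the visit and the sample was drawn within an upper limit since the last dose, for example 144 to 192 h. List all other concentrations without summarizing them as Ctrough. At Visit 9, apply the window before choosing the sample closest to 168 h.

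The 192 h limit is a proposal, not a figure from the documents; it mirrors the SAP's own 24 h tolerance around 168 h. The treatment condition alone would leave missed-dose samples in. Its wording should keep completers at Visit 12, whose treatment ends at that visit.

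The cost is one SAP sentence. Dose dates and times are in the diary (Protocol 6.4.1) and actual sample times are recorded (Protocol 8.6), so no new data are needed. The downside is slightly fewer trough values, mainly in the EOT row.
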